2 INTRODUCTION

2.1 STUDY RATIONALE

There is currently a significant need for an accessible diagnostic measure to facilitate early diagnosis and treatment management of subjects with neurodegenerative diseases associated with amyloidogenic proteinopathy, such as Parkinson's disease, multiple system atrophy (MSA), and amyotrophic lateral sclerosis (ALS).

AMDX-2011P is a novel retinal tracer indicated for the detection of alpha-synucleinopathies (α -syn) in Parkinson's disease and MSA, and transactive response DNA-binding protein 43 (TDP-43) in ALS. AMDX-2011P is a phosphate prodrug hydrolyzed in vivo to the pharmacologically active molecule, AMDX-2011.

Nonclinical studies have demonstrated that AMDX-2011 binds selectively to protein with high beta sheet content, such as retinal amyloid beta, α -syn, and TDP-43 deposits associated with human amyloid-related diseases. When AMDX-2011 binds to amyloid or amyloid-like peptides, it fluoresces with excitation and emission wavelengths, enabling visualization of amyloid deposits through conventional retinal imaging instruments widely available in ophthalmology clinics.

Pharmacokinetic (PK) studies in rats and dogs demonstrated rapid and incomplete hydrolysis of AMDX-2011P to AMDX-2011 in plasma; and only AMDX-2011 (and not AMDX-2011P) was quantifiable in retinal tissues in rats after intravenous (IV) administration. After a bolus IV injection of 15 mg/kg, a pharmacologically active dose of AMDX-2011P in rats, peak AMDX-2011 concentrations were achieved in the retina by 2 minutes postdose and were below the level of detection within 30 minutes postdose. Similarly, in rabbits, after an IV injection of 15 mg/kg AMDX-2011P, only AMDX-2011 was detected in the retina, and the majority of AMDX-2011 was cleared from the retina within 60 minutes.

The safety of AMDX-2011P has been evaluated in a program of Good Laboratory Practice (GLP) toxicology and safety pharmacology studies, conducted using a single bolus IV injection of AMDX-2011P to mimic the clinical dosing regimen. In the definitive GLP single-dose rat study, no adverse target organ toxicity and no evidence of ocular or cutaneous phototoxicity were identified at up to 50 mg/kg. Injection site reactions occurred in rats after administration into the tail vein, which were considered adverse at 50 mg/kg and not adverse at \leq 15 mg/kg. Therefore, in rats, the dose showing no adverse systemic toxicity was 50 mg/kg, and the overall study no-observed-adverse-effect level (NOAEL) was 15 mg/kg. In safety pharmacology studies conducted in rats, there were no acute neurobehavioral changes or effects on respiratory function at up to 50 mg/kg. In the definitive GLP single-dose dog study, reversible clinical ophthalmic signs, including mydriasis, minimal hyperemic conjunctiva and minimal to mild chemosis, occurred in male dogs within 24 hours postdose at 60 mg/kg. Other non-adverse clinical signs at 60 mg/kg included intermittent emesis and soft feces, which resolved by Day 2 and were not considered adverse. There was histologic evidence of injection site reactions in dogs at all doses, which were not considered adverse. There was no adverse target organ toxicity in dogs at 60 mg/kg, which was considered the NOAEL in females; the NOAEL in males was 20 mg/kg.

based on ophthalmic changes at 60 mg/kg. In a dog cardiovascular safety study, transient reductions in blood pressure (systolic, diastolic, and mean arterial pressure) and heart rate occurred at 15-30 minutes after a single bolus injection of 30 mg/kg, but not at \leq 10 mg/kg, and there were no effects on electrocardiogram (ECG) profile at any dose. In vitro, AMDX-2011 caused a dose-dependent inhibition of the human Ether-à-go-go-related gene (hERG) cardiac potassium channel of up to 44% at a concentration of 10 μ M. This concentration is expected to be at least 10-fold above human peak plasma concentration (C_{max}) values of the pharmacologically relevant doses; therefore, a risk for QTc prolongation in humans is considered low. Overall, the nonclinical safety studies support the safe administration of AMDX-2011P in this study.

The current prospective randomized open, blinded endpoint (PROBE) study is designed to evaluate the ability of AMDX-2011P to assess safety, tolerability, and PK, as well as detect amyloid deposits, α -syn and TDP-43 through retinal imaging following escalating doses of bolus IV AMDX-2011P administration in subjects with Parkinson's disease, MSA and ALS.

2.2 BACKGROUND

2.2.1 Parkinson's Disease

Parkinson's disease is a neurodegenerative disorder that mostly presents in later life with generalized slowing of movements (bradykinesia) and at least one other symptom of resting tremor or rigidity (Zafar, 2021). The prevalence of Parkinson's disease increases with age and is more common in males than females (de Lau, 2006; Dorsey, 2018; GBD, 2018). The neuropathological hallmarks of Parkinson's disease are neuronal loss in the basal ganglia, specifically the substantia nigra and globus pallidus (Prakash, 2016), which leads to striatal dopamine deficiency, and intracellular inclusions containing aggregates of α -syn. Therefore, Parkinson's disease belongs to the group of α -synucleinopathies (including Parkinson's disease, dementia with Lewy bodies and multiple system atrophy) that share the abnormal aggregation of α -syn as their key-molecular hallmark (Malfertheiner, 2021).

Currently, there are no specific tests to detect Parkinson's disease. Diagnosis is determined with a clinical evaluation by identifying and monitoring symptoms associated with the disease. Recent advances in brain imaging (magnetic resonance imaging [MRI], computed tomography [CT], dopamine transport scan [DaTscan]) can only be used to rule out structural and other causes of parkinsonian symptoms (Nemade, 2021).

α -syn is an abundant neuronal protein that is primarily found in the presynaptic nerve terminals (Lashuel, 2013). Under pathological conditions α -syn is phosphorylated and accumulates and forms insoluble aggregates (Heras-Garvin, 2020). Pathological aggregates of α -syn has been reported in retinal layers of Parkinson's disease patients in postmortem examination and levels of α -syn deposition in retina may provide an in vivo indicator of disease severity (Ortuño-Lizarán, 2018). Furthermore, 80% of Parkinson's disease patients report at least one visual symptom that often occurs in early disease stages preceding cardinal Parkinson's disease symptoms and correlates with disease progression (Veys, 2019). However, there are currently no positron emission tomography (PET) ligands that can selectively label α -syn

deposits, and detection is thus far only possible by histological examination of postmortem brain tissue ([Korat, 2021](#)).

2.2.2 Multiple System Atrophy

MSA is a fatal progressive neurodegenerative disease characterized by the variable combination of autonomic dysfunction, parkinsonian and cerebellar features ([Fanciulli, 2015a; Jellinger, 2018](#)). The dominant display of specific symptomatology is used to stratify cases of disease into two subtypes: a parkinsonian variant (MSA-P) associated with features such as bradykinesia, muscle rigidity, tremors, and postural instability, and a cerebellar variant (MSA-C) characterized by cerebellar ataxia, speech difficulties and problems controlling eye movement ([Fanciulli, 2015b](#)). Movement Disorder Society (MDS) criteria for MSA diagnosis were recently updated ([Wenning, 2022](#)); however, MSA and Parkinson's disease can be difficult to differentially diagnose due to large overlaps in presenting symptoms and the lack of specific tests for either condition ([Stankovic, 2019](#)).

MSA is characterized by inclusions of abnormal α -syn protein that, for unknown reasons, build up in cells in many parts of the brain and spinal cord ([Koga, 2021](#)). There are key differences in the nature of α -syn deposition in MSA and Parkinson's disease, and how these manifests in retina. At the cellular level, MSA is distinguished from Parkinson's disease in that α -syn deposits occur almost exclusively as cytoplasmic inclusions in oligodendrocytes – so called “glial cytoplasmic inclusions” ([Koga, 2018; Schweighauser, 2020](#)). Oligodendrocytes are excluded from the retina (presumably to avoid light scattering effects of myelination) but line the retrolaminar aspect of the optic nerve. In addition, recent data indicate that amyloid configurations of α -syn may differ among synucleinopathies ([Meade, 2019](#)), which may yield different fluorescence emission profiles for each disease. Detecting α -syn early (before symptoms arise) and being able to determine whether it represents Parkinson's or MSA would be a tremendous advance in the field. It would enable earlier and more accurate therapeutic intervention, and greatly facilitate the clinical testing of novel, disease-modifying therapeutics ([Osaki, 2009; Stankovic, 2019; Wenning, 2022](#)).

2.2.3 Amyotrophic Lateral Sclerosis

ALS is the most common adult-onset motor neuron disease, clinically and pathologically characterized by degeneration of upper and lower motor neurons leading to progressive paralysis and death within 3–5 years of diagnosis ([Dhasmana, 2021](#)). The estimated prevalence of ALS in the United States (US) and Europe is 5 cases per 100,000 population ([Chiò, 2013; Mehta, 2018](#)).

TDP-43 inclusions occur in neurons and glia in approximately 97% of ALS cases ([de Boer, 2020](#)). TDP-43 is a DNA/RNA-binding protein that has various roles in RNA metabolism, including trafficking, splicing, and degradation. Misfolding of TDP-43 into an “amyloid-like” or true amyloid configuration promotes aggregate assembly and prion-like spread ([McAlary, 2019; Jo, 2020](#)).

Currently, there are no specific tests to detect ALS. The diagnosis is determined by excluding other conditions and utilizing clinical examinations, laboratory and genetic tests and nerve conduction/needle electromyography studies. Needle electromyography records abnormal

activities at rest and looks for neurogenic patterns during muscle contraction. Motor evoked potentials after transcranial magnetic stimulation remain the test of choice to identify impairment of upper motor neurons ([Štětkářová, 2021](#)). Recent advances in brain imaging (MRI and PET) can only be used to rule out other neurodegenerative diseases. There are no PET ligands that can selectively label TDP-43 deposits ([Young, 2020](#); [Rao, 2021](#)).

2.2.4 AMDX-2011P Product Development

AMDX-2011P is a small molecule intended for IV administration. AMDX-2011P is a prodrug and rapidly converts to AMDX-2011, its active moiety, after injection. In vitro and in vivo pharmacology studies have demonstrated that AMDX-2011 binds to human brain and α -syn associated with Parkinson's disease and MSA, and TDP-43 in ALS.

In vivo studies in mice indicated that amyloidogenic deposits in the retina can be visualized as hyper-fluorescent signals after systemic doses of AMDX-2011P. The principle for the sensitive and selective detection of amyloid-like peptides by AMDX-2011 and other molecules sharing the same molecular core is the enhanced fluorescence occurring after binding ([Cao, 2018](#)). Compound binding to the beta-pleated sheet structure of the peptide increases fluorescence by restricting the torsional rotation of the sigma bond between the piperidine and naphthalene rings and enhancing the electronic transition upon photoexcitation. The primary de-excitation mechanism of enhanced fluorescence can then be detected visually.

A detailed description of the chemistry, pharmacology, efficacy (activity), and safety of AMDX-2011P is provided in the Investigator's Brochure (IB).

2.3 RISK/BENEFIT ASSESSMENT

Detailed information about the known and expected benefits and risks and reasonably expected adverse events of AMDX-2011P may be found in the IB.

2.3.1 Known Potential Risks

This is the first-in-human (FIH) study with AMDX-2011P. Though similar and higher doses of AMDX-2011P have been tested in multiple animal studies and results support the dose level to be tested in humans, this will be the first clinical exposure of the study drug; thus, there may be risks that are currently unknown.

There are no identified or potential risks of particular severity or seriousness anticipated on the basis of the mechanism of action of AMDX-2011P. The potential risks are based on theoretical considerations and findings ([Table 2](#)) from completed GLP nonclinical safety studies.

Table 2 Risk Assessment

Potential Risk of Clinical Significance	Summary of Data/Rationale for Risk	Mitigation Strategy
Potential Risks which may be associated with Study Drug		
Phototoxicity	Both AMDX-2011P and AMDX-2011 were suspected of being phototoxic in the in vitro	Subjects will be instructed to avoid direct sunlight and wear

Potential Risk of Clinical Significance	Summary of Data/Rationale for Risk	Mitigation Strategy
	3T3 neutral red uptake phototoxicity test; however, there was no evidence of ocular or cutaneous phototoxicity after IV administration of AMDX-2011P to pigmented rats at doses of up to 50 mg/kg followed by exposure to ultraviolet B, ultraviolet A, and visible light from a xenon lamp.	protective gear (e.g., sunglasses) for 24 hours after dosing. Ophthalmologic examinations will be conducted throughout the study.
Effect on eye	In male dogs, single IV bolus injections of 60 mg/kg AMDX-2011P resulted in mydriasis, minimal hyperemic conjunctiva and minimal to mild chemosis within 24 hours postdose, which was reversible within 6 days.	Ophthalmologic examinations will be conducted throughout the study.
Effect on cardiovascular function	In dogs, single IV bolus injections of 30 mg/kg AMDX-2011P resulted in transient reductions in systolic, diastolic, and mean arterial pressure and heart rate 15-30 min after injection. In vitro, inhibition of hERG channel was seen at high concentrations of AMDX-2011P.	Vital sign assessments, triplicate ECG recording
Mutagenicity	AMDX-2011P and AMDX-2011 were mutagenic in bacteria only in the presence of an exogenous metabolic system, suggesting a metabolite was the mutagenic and not the parent drugs. AMDX-2011P and AMDX-2011 did not cause chromosomal aberrations in mammalian cells with or without metabolic activation.	Healthy volunteers are excluded from clinical studies until additional information on human risk is obtained.

Potential Risks which may be associated with Study Procedures

Injection site reactions (ISRs) such as redness, swelling, itching and tenderness	As with any IV administration procedure, ISR is possible. ISRs were seen in nonclinical studies (rats)	IV administration will be done by trained personnel. In the case of ISRs, observe and treat as needed.
Retinal imaging.	Potential mild discomfort, fatigue and temporary dry eyes	For temporary dry eyes, artificial tears may be used to alleviate the symptoms. Retinal imaging will be performed by trained personnel to minimize the time of data acquisition.

Abbreviations: ECG, electrocardiogram; hERG, human Ether-à-go-go-related gene; ISR, injection site reaction; IV, intravenous

2.3.2 Known Potential Benefits

The results from completed nonclinical studies with AMDX-2011P suggest a potential benefit of AMDX-2011P as a novel compound to facilitate diagnosis and patient management in these conditions.

2.3.3 Assessment of Potential Risks and Benefits

Considering the measures taken to minimize risk to subjects participating in this study, the potential risks identified in association with AMDX-2011P are justified, given the significant need for an accessible diagnostic measure for patients with neurodegenerative diseases.

3 OBJECTIVES AND ENDPOINTS

OBJECTIVES	ENDPOINTS
Primary	

 • To assess safety and tolerability of single intravenous (IV) dose of AMDX-2011P in subjects with neurodegenerative diseases (Parkinson's disease, MSA and ALS). 	
 • Incidence, nature, and severity of adverse events (AEs) and serious adverse events (SAEs).
Secondary	

 • To assess the ability of AMDX-2011P to identify α-syn in retina of subjects with Parkinson's disease or MSA. • To assess the ability of AMDX-2011P to identify TDP-43 in retina of subjects with ALS. • To characterize the PK profile of AMDX-2011P and AMDX-2011 following administration of a single IV dose of AMDX-2011P in subjects with neurodegenerative diseases (Parkinson's disease, MSA and ALS). 	
 • Detection of α-syn in the retina after AMDX-2011P administration. • Detection of TDP-43 in the retina after AMDX-2011P administration. • The PK parameters of AMDX-2011P and AMDX-2011 calculated from concentrations in plasma.

4 STUDY DESIGN

4.1 OVERALL DESIGN

This is a PROBE study designed to evaluate safety, tolerability, and the ability of AMDX-2011P to detect amyloid deposits, α -syn and TDP-43 (collectively called amyloidogenic deposits) through retinal imaging, as well as PK of single bolus IV of AMDX-2011P in subjects with Parkinson's disease, MSA and ALS. Study schema is shown in Section 1.2.

The study will enroll up to 4 dose cohorts, as shown in Table 3:

Table 3 Cohorts and Planned Doses

Cohort	Number of Subjects with neurodegenerative diseases (Parkinson's Disease and/or MSA and/or ALS) ^a	Proposed dose level
1	3-9 ^b	25 mg (1 mL)
2	3-9 ^b	50 mg (2 mL)
3	12 ^b	100 mg ^c (4 mL)
4	12 ^b	150 or 200 mg ^c (6-8 mL)

Abbreviation: ALS, amyotrophic lateral sclerosis; SMC, Safety Monitoring Committee; TBD, to be determined.

a. Additional subjects (from any subject population) may be enrolled into any cohort per SMC discretion.

Approximately 9 ALS subjects will be enrolled in the study. Approximately 9 MSA subjects will be enrolled.

b. All cohorts will include 1 sentinel subject who will be observed for 8 hours and evaluated at 24 hours for safety before enrolling the remaining subjects in that cohort.

c. Tentative dose and will be confirmed by SMC based on emerging data from the prior cohorts; intermediate or higher dose level may also be explored in these cohorts.

A Safety Monitoring Committee (SMC), comprised of the Study Medical Monitor (or designee), neurologists with experience in these diseased populations, an ophthalmologist with retinal imaging expertise, and the Sponsor's clinical and technical representatives, will review safety data throughout the study. The SMC may recommend modifying the duration of observation or timing of study procedures based on safety and other available data from the first cohort. For additional details, refer to Section 10.1.5.

All cohorts will include subjects with neurodegenerative diseases (Parkinson's disease, MSA and/or ALS). The decision to escalate to the next dose level will be made based on review of all available safety and tolerability data collected, including AEs, ECGs, vital signs, and laboratory safety results of the previous dose levels after single dose administration in at least 3 subjects from each cohort. Based on emerging data, additional cohort(s) and/or an intermediary dose may be investigated with prior approval by the SMC. The study may progress to the next cohort if approved upon satisfactory review of available safety data of the previous cohort(s) by the SMC. During each safety review, the SMC will make a decision to either continue enrollment to the next planned cohort, add additional subjects to the current cohort, or change the dose of the next cohort.

Enrollment into each cohort will begin with 1 sentinel subject who will be observed for at least 8 hours at the clinic and evaluated by the investigator at 24 hours following dosing by the investigator. If no safety issues are observed, the remaining subjects will be enrolled into that cohort. Dosing of remaining subjects at the same center will be staggered by at least 1 hour. Dosing within a cohort will continue unless stopping rules are met.

For all dose cohorts, after signing the informed consent, subjects will be screened. If needed, the screening procedures may occur over a period of up to 42 days prior to dosing. On Day 1, subjects will be admitted to the clinical research unit for 8 hours confinement. Eye examination and retinal imaging will be conducted before administration of the study drug. AMDX-2011P will be administered through a single IV bolus injection followed by repeated retinal imaging and PK and safety assessments as outlined in the Schedule of Activities (SoA; Section 1.3). On Day 8 (end of study), there will be a follow-up visit for retinal imaging and safety assessments.

All retinal images will be deidentified and sent in batched to a reading center for masked assessment. Assessors will be masked to type of subjects, their disease, dose, clinical status of subjects, and sequence of post-injection images. This provides an objective assessment of the ability of AMDX-2011P to identify amyloidogenic deposits. During the interim analysis (see Section 9.3.8), the SMC may also review representative images to confirm the optimum detection and the residence time and make potential recommendations to the retinal imaging timepoint(s) and/or potential safety assessment modifications.

4.3 JUSTIFICATION FOR DOSE

The proposed starting dose is based on recommendations from an FDA Guidance for Industry: *Estimating the Maximum Safe Starting Dose in Initial Clinical Trials for Therapeutics in Adult Healthy Volunteers, July 2005* (FDA, July 2005). Table 4 shows NOAEL doses and systemic AUC and C_{max} exposures from the pivotal rat and dog toxicity studies, as well as projected human exposures at proposed clinical dose levels. Clinical PK parameters (clearance and volume of distribution) for AMDX-2011P were projected by model fitting of dog PK data, then scaling to human values. AMDX-2011 parameters were projected based on rates of formation and

observed metabolite/parent ratios in animals. Human PK profiles were then simulated at various doses based on projected parameter values.

The lowest NOAEL for dogs (20 mg/kg, males) equates to a human equivalent dose (HED) for a 60-kg adult male of 667 mg, and the NOAEL for systemic toxicity in rats (50 mg/kg) equates to a HED of 484 mg. Using an ~20-fold safety margin, the starting dose in the proposed clinical study will be 25 mg. The escalating doses will be 25 mg, 50 mg, 100 mg, and either 150 mg or 200 mg.

The doses proposed for this study will cover the anticipated pharmacologically active dose range and are predicted to be significantly below AUC and C_{max} exposures for AMDX-2011 and AMDX-2011P achieved at NOAEL doses in rats and dogs.

Table 4 Projected Human Dose Levels and Corresponding AUC and C_{max} Exposures Based on Nonclinical Data

Dose	AUC (hr •ng /mL)		C_{max} (ng/mL)	
	AMDX-2011P^a	AMDX-2011^a	AMDX-2011P^a	AMDX-2011^a
Human (mg)				
25	49.0	19.1	135	43.8
50	97.8	38.2	269	87.5
75	144	57.4	403	131
100	192	76.6	539	175
150	288	115	806	263
200	383	153	1070	350
Dog NOAEL^b				
20 mg/kg (Male) (HED 667 mg)	400	182	2270	937
60 mg/kg (Female) (HED 2000 mg)	13,700	2200	45,500	5930
Rat NOAEL^c				
15 mg/kg (injection site reaction) (HED 145 mg)	923	138	7,175	1,019
50 mg/kg (Systemic) (HED 484 mg)	17,900	1,345	141,500	8,930

^a human AUC and C_{max} values are estimated from projected PK at each dose level

^b NOAEL in dogs based on ophthalmic clinical observations at 60 mg/kg in males and no adverse toxicity in females. AUC values are AUC_{last}

^c NOAEL in rats based on adverse injection site reactions at 50 mg/kg, but no adverse target organ (systemic) toxicity at up to 50 mg/kg. AUC_{last} and C_{max} are means of male and female values.

Abbreviation: AUC, area under the curve; HED, human equivalent dose; NOAEL, no observed adverse effect level.

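### Protocol Section 4.3 says the planned doses stay well below NOAEL exposures, but Table 4 puts the AUC margin at 200 mg at about 1

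*Protocol*

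**What the plan says.** Section 4.3 sets out the dose range: "The escalating doses will be 25 mg, 50 mg, 100 mg, and either 150 mg or 200 mg". It then summarises the exposure margins in one sentence, which begins: "The doses proposed for this study will cover the anticipated pharmacologically active dose range and are predicted to be significantly below AUC". Read to its end, the sentence says that these doses "are predicted to be significantly below AUC and C_{max} exposures for AMDX-2011 and AMDX-2011P achieved at NOAEL doses in rats and dogs". No dose, analyte, metric, species or particular NOAEL is excepted.

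Table 4 follows, with projected human AUC and Cmax by dose and the animal values at four NOAEL rows. Two rows matter most here:

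- Male dog, "20 mg/kg (Male) (HED 667 mg". The table footnote bases this on ophthalmic observations at 60 mg/kg.
- Rat, "15 mg/kg (injection site reaction) (HED 145 mg". Protocol Section 2.1 calls 15 mg/kg the overall NOAEL of the rat study.

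Table 2 (Section 2.3.1) lists effect on the eye as a risk: "In male dogs, single IV bolus injections of 60 mg/kg AMDX-2011P resulted in mydriasis, minimal hyperemic conjunctiva and minimal to mild chemosis". Footnote c to Table 3 (Section 4.1) makes the doses for Cohorts 3 and 4 tentative and adds that an "intermediate or higher dose level may also be explored in these cohorts".

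**The concern.** The summary sentence and the table beneath it do not agree at the top of the dose range. The only margin the text puts a number on is the roughly 20-fold one for the 25 mg starting dose, which is on human equivalent dose. A reader who meets that figure and then the summary sentence would take the AUC margin for Cohort 4 to be large. Table 4 lists exposures and not ratios, so the reader has to divide to find otherwise.

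The row that comes closest is the one set by eye signs, and the product is a retinal tracer with eye effects among its listed risks. The statement is therefore loosest where an IRB, an investigator or the Safety Monitoring Committee (SMC) would most want it to be exact.

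**Working it through.** **The plan's own figure.** The starting-dose margin reproduces: 484/25 = 19.4, or about 20-fold. The human equivalent doses are also consistent with one another. The divisor implied for a 60-kg adult is 20 × 60/667 = 1.80 and 60 × 60/2000 = 1.80 for the dog, and 50 × 60/484 = 6.20 and 15 × 60/145 = 6.21 for the rat. Nothing is wrong there.

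**Inputs, all from Table 4** (AUC in hr·ng/mL, Cmax in ng/mL):

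| Row | AUC 2011P | AUC 2011 | Cmax 2011P | Cmax 2011 |
|---|---|---|---|---|
| Human 150 mg | 288 | 115 | 806 | 263 |
| Human 200 mg | 383 | 153 | 1070 | 350 |
| Male dog 20 mg/kg | 400 | 182 | 2270 | 937 |
| Rat 15 mg/kg | 923 | 138 | 7175 | 1019 |
| Female dog 60 mg/kg | 13,700 | 2200 | 45,500 | 5930 |
| Rat 50 mg/kg | 17,900 | 1345 | 141,500 | 8930 |

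**Formula.** Margin = NOAEL exposure / projected human exposure. A value below 1 means the projected human exposure is above the NOAEL exposure.

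**At 200 mg:**

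| NOAEL | AUC 2011P | AUC 2011 | Cmax 2011P | Cmax 2011 |
|---|---|---|---|---|
| Male dog 20 mg/kg | 400/383 = 1.04 | 182/153 = 1.19 | 2270/1070 = 2.12 | 937/350 = 2.68 |
| Rat 15 mg/kg | 923/383 = 2.41 | 138/153 = 0.90 | 7175/1070 = 6.71 | 1019/350 = 2.91 |

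Against female dog 60 mg/kg and rat 50 mg/kg the lowest margin is 1345/153 = 8.79. Of the 16 comparisons at 200 mg (four NOAEL rows, two analytes, two metrics), one is an exceedance, the 0.90.

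**At 150 mg** the three lowest margins are all for AUC:

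- rat 15 mg/kg, AMDX-2011: 138/115 = 1.20
- male dog, AMDX-2011P: 400/288 = 1.39
- male dog, AMDX-2011: 182/115 = 1.58

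**At lower doses** the lowest margin of any kind comes from AMDX-2011 AUC against rat 15 mg/kg: 138/76.6 = 1.80 at 100 mg, 138/38.2 = 3.61 at 50 mg, and 138/19.1 = 7.23 at 25 mg. Against the male dog alone the lowest are 400/192 = 2.08, 400/97.8 = 4.09 and 400/49.0 = 8.16.

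**Dose at which projected AUC equals the NOAEL value.** This assumes linear scaling from the 200 mg row. Projected AUC per mg for AMDX-2011P is 1.92 to 1.96 across the table, so linearity fits the projections. The two doses above 200 mg extrapolate beyond the table.

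- male dog, AMDX-2011P: 200 × 400/383 = about 209 mg
- male dog, AMDX-2011: 200 × 182/153 = about 238 mg
- rat 15 mg/kg, AMDX-2011: 200 × 138/153 = about 180 mg

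**The case against.** Several points can be made for the plan, and some of them stand.

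- **The rat 15 mg/kg row concerns a local reaction.** Systemic AUC says little about injection-site tolerance, and the paragraph before the sentence works from the male-dog and rat 50 mg/kg NOAELs. This stands as a reason to give the 0.90 little weight. It does not rescue the sentence, because the male-dog row alone gives 1.04 and 1.19.
- **At 150 mg every projected value is below every NOAEL value, and the plan sets no threshold for its wording.** This stands. The 150 mg part of the point is weaker and partly a matter of judgement.
- **A margin to a NOAEL is not a margin to an effect.** The dog eye signs appeared at three times the male NOAEL dose and were reversible. Table 4 gives no male exposure at 60 mg/kg, so the distance to the effect is unknown. On human equivalent dose, 200 mg has margins of 667/200 = 3.3 and 484/200 = 2.4 (although 145/200 = 0.73 for rat 15 mg/kg). All true, but the sentence is about AUC and Cmax at the NOAEL.
- **Escalation does not depend on the sentence.** The 200 mg dose is tentative and needs SMC confirmation, sentinel dosing and stopping rules apply, the SMC includes an ophthalmologist, and eye examinations run through the study. Section 9.3.8 also schedules an interim look at PK after Cohort 2 or 12 subjects. This limits the consequence. However, Section 10.1.5 has the SMC review PK only when it is available, so observed exposure is not a required input to the Cohort 4 decision.
- **The table is printed directly below.** That makes the conflict easy to find, but text and table still cannot both stand.

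**Conclusion.** The concern holds. For AUC at 200 mg the statement in Section 4.3 is contradicted by Table 4: projected exposure is 95.8% (383/400) and 84.1% (153/182) of the male-dog NOAEL values, and for AMDX-2011 it is 110.9% (153/138) of the rat 15 mg/kg value. At 150 mg the support is thin but nothing is exceeded. The wording is fair for 25 and 50 mg, and for every comparison with the female-dog and rat 50 mg/kg rows. Cmax margins at 200 mg are at least 2.1.

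This takes Table 4 as printed. The human figures are model projections for which the protocol gives no error. The animal AUCs are to the last measurable concentration, and the type of human AUC is not stated. No table entry is shown to be miscalculated, the starting dose is not in question, and nothing here shows 200 mg to be unsafe. The fault is an overstated margin in a first-in-human dose justification. It should be corrected, though the existing safeguards limit what follows from it.

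**What to change.** Replace the sentence with a table of fold-margins by dose, analyte, metric and NOAEL, taken from Table 4. State plainly that at 200 mg the AUC margin against the male-dog ophthalmic NOAEL is about 1, and that AMDX-2011 AUC is above the rat 15 mg/kg (injection-site) value. Justify 150 to 200 mg, and any higher dose allowed by footnote c of Table 3, on those figures. Require that the SMC receive the same margin table, updated with observed human PK from the earlier cohorts, when it sets the Cohort 4 dose.

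The cost is a protocol text amendment with IRB review. The margins on the page become less favourable and may draw questions about 200 mg. Visits, sample size and analysis do not change.
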